2 LIST OF ABBREVIATIONS

LIST OF ADDREVIATIONS				
Term	Definition / description			
(e)CRF	(electronic) Case Report Form			
(m)RNA	(messenger) RiboNucleic Acid			
(T)SAP	(Trial) Statistical Analysis Plan			
ADA	Anti-Drug Antibody			
ADS	Analysis Data Set			
AE	Adverse Event			
AESI	Adverse Event of Special Interest			
ALKP	Alkaline Phosphatase			
ALT	Alanine Aminotransferase			
ANOVA	Analysis Of Variance			
AR-V7	Androgen Recept Variant 7			
AST	Aspartate Transaminase			
ATC	Anatomical, Therapeutic, Chemical (classification system)			
AUC	Area Under the plasma concentration-time Curve			
$AUC_{\tau,ss}$	Area under the plasma concentration-time curve over the dosing interval at steady state			
AUEC	Area Under the Effect Curve			
BB	Blood Biomarker Set			
BI	Boehringer Ingelheim			
BIcMQ	BI customised MedDRA Queries			
BIRDS	Boehringer Ingelheim Regulatory Documents for Submission			
BLQ	Below lower Limit of Quantification			
BMI	Body Mass Index			
BPI-SF	Brief Pain Inventory Short Form			
BRPM	Blinded Report Planning Meeting			
BS	Biomarkers Set			
BSA	Body Surface Area			
C	Cycle			
cfDNA	cell-free DNA (DeoxyriboNucleic Acid)			
$C_{\text{max,ss}}$	Maximum measured plasma concentration at steady state			

Term	Definition / description
C _{pre,ss}	Pre-dose plasma concentration at steady state
CR	Complete Response
CRPC	Castration-Resistant Prostate Cancer
CSAP	Cumulative Statistical Analysis Plan
CSD	Company Standard Displays
CT	Concomitant Therapy
CTC	Circulating Tumour Cell
CTCAE	Common Terminology Criteria for Adverse Events
CTCb	CTC biomarker set
CTP	Clinical Trial Protocol
CTR	Clinical Trial Report
DBL	Database Lock
DC	Disease Control
DCS	Downstream Cascade Set
DILI	Drug-Induced Liver Injury
DLT	Dose Limiting Toxicity
DMS	Data Management and Statistics
ECG	Electrocardiogram
ECG-PK	ECG-PK analysis set
ECGS	ECG Set
E_{max}	E _{max} model (PD/PD model)
ENR	Enrolled Set
EOT	End of Treatment
EOT(V)	End of Treatment (Visit)
EWB	Emotional Well-Being (subscale score)
FACIT	Functional Assessment of Chronic Illness Therapy
FACT-G	Functional Assessment of Cancer Therapy - General
FACT-P	Functional Assessment of Cancer Therapy - Prostate
FDA	Food and Drugs Administration
FFPE	Formalin Fixed Paraffin Embedded
FU	Follow-up

Term	Definition / description
FWB	Functional Well-Being (subscale score)
HR	Hazard Ratio / heart rate
ICH	International Conference on Harmonisation
IGF	Insulin Growth Factor
IGF-1	Insulin Growth Factor 1
IGF-2	Insulin Growth Factor 2
IGFBP-3	Insulin Growth Factor Binding Protein 3
IHC	Immunohistochemistry
IPV	Important Protocol Violation
IRT	Interactive Response Technology
ITT	Intent-to-Treat
LLOQ	Lower Limit of Quantification
LLT	Lowest Level Term
LS Means	Least-Squares Means
Max	Maximum
MedDRA	Medical Dictionary for Regulatory Activities
Min	Minimum
MMRM	Mixed-effects Model for Repeated Measures
MQRM	Medical Quality Review Meeting
MRI	Magnetic Resonance Imaging
mRNAS	mRNA set
MS	MTD Set
MSb	Mutational status biomarker set
MTD	Maximum Tolerated Dose
NCA	Noncompartmental Analysis
NCI	National Cancer Institute
ND	No Disease
NE	Not Evaluable
OS	Overall Survival
pAkt	phosphor Akt
PCS	Prostate Cancer Subscale score

Term	Definition / description
PCWG2	Prostate Cancer Clinical Trials Working Group 2
PD	Progressive Disease / Pharmacodynamic (as applicable)
PES	Protein Expression Set
PFS	Progression Free Survival
PK	Pharmacokinetics
PKS	Pharmacokinetics Set
PPS	Per Protocol Set
PR	Partial Response
PR interval	ECG interval from the onset of the P wave to the beginning of the QRS complex
PRP	Platelet-Rich Plasma
PSA	Prostate-Specific Antigen
PT	Preferred Term
PTEN	Phosphatase and Tensin Homolog
PV	Protocol Violation
PWB	Physical Well-Being (subscale score)
Q1	25 th percentile
Q3	75 th percentile
QOL	Quality of Life
QRS	Combination of the Q, R and S waves
QT	ECG interval from the beginning of the QRS complex to the end of the T wave
QTc	Generic term for QTcF and QTcB intervals
QTcB	QT interval, corrected by Bazett's formula
QTcF	QT interval, corrected by Fridericia's formula
RD	Reference Document
RECIST	Response Criteria In Solid Tumours
REP	Residual Effect Period
RP2D	Recommended Phase II Dose
RPM	Report Planning Meeting
RS	Randomised Set
SAE	Serious Adverse Event

Boehringer Ingelheim

TSAP for BI Trial No.: 1280.8 Page 10 of 76

Term	Definition / description
SAP	Statistical Analysis Plan
SAS	Statistical Analysis System
SD	Stable Disease / Standard Deviation
SIR	Synoptic Interim Report
SMQ	Standardised MedDRA Queries
SOC	System Organ Class
SOP	Standard Operating Procedure
SPOP	Speckle-type POZ Protein
SS	Steady state
SWB	Social/Family Well-Being (subscale score)
TCM	Trial Clinical Monitor
t_{max}	The time after dosing when C _{max} occurs
TMCP	Translational Medicine and Clinical Pharmacology
TOI	FACT-P Trial Outcome Index
TS	Treated Set
UDAEC	User Defined Adverse Events Categories
ULN	Upper Limit of Normal
URPM	Unblinded Report Planning Meeting
V	Visit
VT	Virtual Twins
WHO-DD	World Health Organisation Drug Dictionary

3 INTRODUCTION

As per International Conference on Harmonisation (ICH) E9 (5), the purpose of this document is to provide a more technical and detailed elaboration of the principal features of the analysis described in the protocol, and to include detailed procedures for executing the statistical analysis of the primary and secondary variables and other data.

This Trial Statistical Analysis Plan (TSAP) assumes familiarity with the Clinical Trial Protocol (CTP), including Protocol Amendments. In particular, the TSAP is based on the planned analysis specification as written in CTP (see in section "Statistical Methods and Determination of Sample Size"). Therefore, TSAP readers may consult the CTP for more background information on the study, e.g., on study objectives, study design and population, treatments, definition of measurements and variables, planning of sample size, randomisation. This TSAP follows Boehringer Ingelheims (BI) internal reference (1).

The trial consists of three parts, the phase Ib including the dose escalation part and the expansion cohort and phase II including the randomised part.

The TSAP describes the analysis for all parts of the trial. After the phase I escalation part, safety analyses were performed and documented in a Synoptic Interim Report (SIR) (see Section 9.1).

In general, study or trial medication refers to the combination of xentuzumab with enzalutamide, as well as the monotherapy of the aforementioned medications.

Statistical Analysis System (SAS) Version 9.4 or later version will be used for all analyses unless otherwise specified.

4 CHANGE IN THE PLANNED ANALYSIS OF THE STUDY

4.1 ADDITIONS/NEW ANALYSES

Skeletal events are analysed by investigator assessment and by central review assessment. Only the endpoint "time to first skeletal event" related to investigator assessment was planned in the protocol. The endpoint associated to central review assessment has been added in the further endpoints.

The endpoint Disease Control (DC) has been added in further endpoints.

4.2 CHANGES

There is one change in the assessment of target lesions according to Response Criteria In Solid Tumours version 1.1 (RECIST 1.1) (R09-0262) which is applied by the central review in this trial and which is described in the imaging charter. More details can be found in Section 5.2.2.3 of this TSAP.

Several criteria are used to analyse CTCs. The following one was not planned in the protocol, but will be analysed along with the other CTC criteria: "CTC status at week 12".

Prostate-Specific Antigen (PSA) endpoints (response, progression): definitions in this TSAP might be slightly different as the ones from the protocol. They have been reworked using the Prostate Cancer Clinical Trials Working Group 2 (PCWG2) guidelines (R13-1642), previous studies and medical knowledge. They are therefore more accurate and include more details in the TSAP.

4.3 CLARIFICATIONS

The following points warrant further clarification:

- If not stated otherwise, date of randomisation will be replaced by first treatment administration of any study medication in the outputs for the Phase Ib part of this trial.
- The terms "progression", "progressive disease" (PD) and "disease progression" will be used interchangeably within this document.
- The terms "treatment cycle" or "treatment course" will be used interchangeably throughout this document.
- The terms "study medication" and "trial medication" will be used interchangeably throughout this document. These terms may be used for the combination of enzalutamide and xentuzumab, or any of these medications alone. Clarification is given when necessary.
- According to the current TSAP template, "Other endpoints" described in the CTP are now named "Further endpoints".

4.4 CLARIFICATIONS TO THE PRIMARY ANALYSIS

The protocol (Section 7.3.1) mentions that the primary analysis will be conducted approximately 23 months after first patient was randomized in phase II part, in case 60 Progression Free Survival (PFS) events are not reached. According to the Table 7.6:3 from the protocol, the calculated duration was actually 22.5 months. The impact of this difference in terms of PFS events is negligible, and it has therefore been decided and agreed to perform this primary analysis 22.5 months after first patient randomized, in case 60 events are not reached.

The protocol (Section 4.1.5.1) states as well that "the BI study team will be blinded for the aggregated phase II data at the treatment level until the trial database lock". The trial and project team clarified and agreed that it is meant until the trial database lock (DBL) of the primary analysis. Indeed, there is no additional blinded team planned for this trial and almost all patients will be off-treatment at that time. The BI study team will therefore be completely unblinded after DBL of the primary analysis.

5 ENDPOINTS

5.1 PRIMARY ENDPOINTS

Best overall response to trial medication will be determined separately according to RECIST version 1.1 (see Appendix 10.4 of the CTP) and to PCWG2 criteria, recorded from first administration of trial medication until the earliest of disease progression, death or last adequate tumour assessment before new anti-cancer therapy. Details about derivation of best overall response are given in Section 5.4.7.

5.1.1 Phase Ib escalation

The primary endpoint is the maximum tolerated dose (MTD) of trial medication based on the occurrence of dose limiting toxicity (DLT) during the first treatment course. The planned treatment course consists of 28 days.

MTD:

MTD is defined as the highest dose level examined of trial medication, at which no more than 1 out of 6 patients experienced a DLT during the MTD evaluation period. The MTD evaluation period is defined as the time from the first administration of xentuzumab up to start of cycle 2. That means that the exact duration of this period will be derived for each patient. If the patient does not start cycle 2, a fixed duration of 28 days will be used.

The MTD and the safety profile (including DLTs occurring after first treatment course), will be the basis to define the recommended phase II dose (RP2D) to be used for further parts of this trial as well as further trials in the development of xentuzumab in combination with enzalutamide.

5.1.2 Phase Ib expansion cohort

The primary endpoint of the phase Ib expansion cohort is the PSA response.

A PSA response in a patient is defined as a decline in PSA value >50% compared to baseline (which is confirmed by the next available value occurring at least 3 weeks later) (R13-1642). The confirmatory value should be at least 50% lower than the baseline, but may be higher than the first PSA value taken into account for response. However the confirmatory value may not be 50% higher than this first PSA. If it is >= 50% higher than the first PSA, the next available sample should be taken to determine if response has been achieved. The date of response is the date that the first 50% (or greater) decline is observed.

Patients without baseline or post-baseline assessments are considered as missing.

Patients presenting with a PSA value showing response but without any confirmatory value will be defined as "unconfirmed responders".

The percentage change from baseline in PSA will be calculated as follows:

• 100*(PSA value post-baseline - PSA value at baseline)/PSA value at baseline

A negative percentage change from baseline shows a decline in PSA.

Some particular data patterns may lead to a patient having PSA progression and PSA response at the same timepoint. Data will be carefully checked in order to detect such assessments. In case further rules are needed, these will as well be discussed at a Blinded Report Planning Meeting (BRPM) or added in a revision of the TSAP.

5.1.3 Phase II

The primary endpoint for the phase II part of the study is PFS based on investigator assessment.

PFS is defined as the time from randomisation until radiological tumour progression in bone (based on PCWG2 criteria) or soft tissue (based on modified RECIST 1.1) or death from any cause, whichever occurs earlier.

Tumour assessments will be performed at screening, week 8, week 16, week 24 and then every 12 weeks thereafter (more details in CTP Flow Chart).

For each follow-up (FU) imaging time-point an overall tumour response will be determined for soft tissue according to modified RECIST 1.1 (R09-0262 and Appendix 10.4 of the CTP) and for bone according to the prostate cancer clinical trials working group (PCWG2) criteria (R13-1642). The overall tumour response for each imaging time-point according to modified RECIST 1.1 will be selected from the following categories: Complete Response (CR); Partial Response (PR); Stable Disease (SD); No disease (ND); Progressive Disease (PD); Non-CR/Non-PD; Not Evaluable (NE). The overall tumour response for each imaging time-point (if clinically indicated) for bone lesion will be selected from the following categories: Non-progressive disease (Non-PD); Progressive disease (PD); Not Evaluable (NE).

Some patients enter the trial without any target or non-target lesion according to RECIST 1.1. Until new lesions appear and a progression is reported for this patient, the response assessment for such patients will be set to No Disease (ND) (see also Section 5.4.7).

For details on the imaging process and RECIST evaluation, see Section 5.1.2 and Section 10.4 of the CTP.

Derivation of endpoint PFS

Derivations below are described in days. However, the endpoints below will be presented in months in the outputs produced for the Clinical Trial Report (CTR).

For patients with 'event' as an outcome for PFS: (according to modified RECIST version 1.1 or PCWG2)

• PFS [days] = date of outcome - date of randomisation + 1.

For patients with 'censored' as an outcome for PFS: (according to modified RECIST version 1.1 or PCWG2)

• PFS (censored) [days] = date of outcome - date of randomisation + 1.

The censoring rules for PFS (i.e. outcome and date of outcome) are given in Table 5.1.3: 1. Clinical disease progression will not be considered for determination of a PFS event, unless the outcome of the progression is death.

Proprietary confidential information © 2017 Boehringer Ingelheim International GmbH or one or more of its affiliated companies

If patients would have their radiological examinations over a number of days, i.e. target lesions assessed on day x, non-target lesions assessed on day y and new lesion (if applicable) on day z, the following rules will be applied:

- If the overall response is PD, the earliest date of multiple assessments will be taken.
- If the overall response is SD, Non-CR/Non-PD, Non PD, PR, CR or NE, the latest of multiple assessment dates will be taken, i.e. in the case of SD, Non-CR/Non-PD, Non PD, PR, CR, the latest of multiple dates will be used to censor the patients.

For PFS according to RECIST and PCWG2, the date of overall response will be determined for RECIST and PCWG2 separately. In case both RECIST and PCWG2 show PD then the date of PD will be the earliest date of these two. When either RECIST or PCWG2 show PD, then the date of outcome will be the date of PD. In case none of RECIST or PCWG2 shows PD then the latest date of RECIST and PCWG2 will be used for censoring.

Imaging assessments for which NE is assigned as the overall response at an imaging time-point are considered to be missed assessments. Please note that NE does not indicate lack of progression.

Table 5.1.3: 1 Derivation rules for PFS

Situation	Outcome (event or censored)	Date of outcome		
No baseline radiological assessment				
Patient with death on or before the second planned radiological assessment	Event	Date of death		
Patient without death or patient with death after second performed radiological assessment	Censored	Date of randomisation (or first treatment administration, in non-randomised trials)		
Without post-baseline radiological assessments				
Vital status is unknown or patient is known to be alive	Censored	Date of randomisation (or first treatment administration, in non-randomised trials)		
Death prior or on the second planned radiological assessment	Event	Date of death		

Table 5.1.3: 1 Derivation rules for PFS (cont.)

Situation	Outcome (event or censored)	Date of outcome
Death beyond the second planned radiological assessment	Censored	Date of randomisation (or first treatment administration, in non-randomised trials)
With baseline and post-batherapy	seline radiological a	ssessments BUT no other anti-cancer
Alive and not progressed, no more than one consecutively missed radiological assessments	Censored	Date of last radiological assessment
Alive and not progressed, two or more consecutively missed radiological assessments	Censored	Date of last radiological assessment prior to missed radiological assessments
Progressed, zero or one missed radiological assessment prior to progression	Event	Date of radiological assessment of progression
Progressed, but two or more consecutively missed radiological assessments prior to progression	Censored	Date of last radiological assessment prior to missed assessment
Death but no progression, zero or one missed radiological assessment prior to death	Event	Date of death

Table 5.1.3: 1 Derivation rules for PFS (cont.)

Situation	Outcome (event or censored)	Date of outcome		
Death without progression, but two or more consecutively missed radiological assessments prior to death	Censored	Date of last radiological assessment prior to missed assessments		
Initiation of subsequent anti-cancer therapy				
Subsequent anti-cancer therapy started before progression or death	Censored	Date of last radiological assessment before subsequent anti-cancer therapy		
No baseline and post- baseline imaging and subsequent-anti cancer therapy started prior to a death	Censored	Date of randomisation (or first treatment administration, in non-randomised trials)		

Data will be carefully checked in order to detect missing assessments. In case further rules are needed, these will be discussed at a BRPM and added in a revision of the TSAP.

In order to identify that consecutive imaging time-points are missing for a given patient, a nominal time point [8, 16, 24, and then every 12 weeks thereafter] will be assigned to the assessments. This is achieved by creating windows for every assessment. The windows are defined in Table 6.7.2: 1.

Last evaluable imaging

An evaluable radiological image for the censoring of PFS is an image for which an overall response assessment of SD, Non-PD, Non-CR/Non-PD, PR or CR has been assigned. This is used for censoring of patients without progression at end of trial, or censoring prior to missed assessments or censoring prior to subsequent anti-cancer therapy. If the bone and the soft tissue assessment have been done at different dates, the date of the first assessment will be the date of censoring.

5.2 SECONDARY ENDPOINTS

5.2.1 Key secondary endpoints

Not applicable.

5.2.2 Other secondary endpoints

5.2.2.1 Phase Ib escalation

There are no secondary endpoints.

5.2.2.2 Phase Ib expansion cohort

Progression-free survival (PFS) based on investigator assessment

The rules are the same as the ones described in Section 5.1.3.

Please note that the date of randomisation will be replaced by the date of the first treatment administration of any study medication.

Changes in CTC response

This is defined as a decline in CTC value from ≥ 5 to ≤ 5 cells per 7.5mL blood (called "specimen volume" within this section and Section 7.5.2.2 (R14-0865), for at least one post-baseline time-point.

Patients with a CTC value <5 cells per 7.5 ml blood at baseline, or with missing baseline value, are not taken into consideration for this endpoint. Patients with no post baseline value are considered as missing for this endpoint.

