5.1.1.1 Phase Ib Expansion Cohort

Primary Endpoint:

PSA response – defined as a decline in PSA value >50% (which is confirmed by a second value 3 to 4 weeks apart)R13 1642.

Secondary Endpoints:

- Radiological progression free survival (PFS) defined as time from start of treatment until disease progression based on investigator assessment:
 - in bone based on the prostate cancer clinical trials working group (PCWG2) criteria, (R13-1642) (see section 5.1.2.1)
 - o or soft tissue, based on modified RECIST 1.1 (R09-0262) where applicable (see Appendix 10.4)
 - o or death.
- Changes in circulating tumour cells (CTC) response CTC reduction compared to baseline for at least one time point after treatment defined as CTC decline from ≥5 to <5 cells per 7.5ml blood (R14-0865)

Phase II Randomised Trial 5.1.1.2

Primary Endpoint:

- Radiological progression free survival (PFS) defined as time from randomisation to disease progression based on investigator assessment:
 - in bone based on the prostate cancer clinical trials working group (PCWG2) criteria, (R13-1642) (see section 5.1.2.1)
 - o or soft tissue based on modified RECIST 1.1 (R09-0262) where applicable (see Appendix 10.4)
 - o or death

Secondary Endpoints:

Radiological progression free survival (PFS) - defined as time from randomisation to disease progression based on central review:

Proprietary confidential information. © 2022 Boehringer Ingelheim International GmbH or one or more of its affiliated companies. All rights reserved.

- o in bone based on the prostate cancer clinical trials working group (PCWG2) criteria, (R13-1642) (see section 5.1.2.1)
- o or soft tissue based on modified RECIST 1.1 (R09-0262) where applicable (see Appendix 10.4)
- o or death
- Overall survival defined as the time from randomisation to death from any cause
- Time to PSA progression defined as the date that a 25% or greater increase in PSA, and an absolute increase of 2 ng/mL or more from the nadir, is documented (which is confirmed by a second value 3 or more weeks later) (R13-1642)
- Maximum decline in PSA compared to baseline that occurs at any point after treatment start
- Percentage change in PSA at week 12 from baseline to week 12 of treatment
- PSA response defined as a decline in PSA value >50% (which is confirmed by a second value 3 to 4 weeks apart)

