- Changes in circulating tumour cells (CTC) response CTC reduction compared to baseline for at least one time point after treatment start separately assessed by two criteria:
 - o CTC decline from ≥5 to <5 cells per 7.5ml blood (R14-0865)
 - Maximum change in CTC counts compared to baseline that occurs at any point after treatment start

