5.1.2.3 Circulating tumour cell (CTC) assessments

Circulating tumour cells will be analysed using the Veridex CellSearch technology. After cell counting, isolated CTCs might be used for morphological, protein or molecular characterization by FISH. CTC counts will be exploratory evaluated as prognostic and surrogate efficacy markers.

Boehringer Ingelheim BI Trial No.: 1280.8 Doc. No.: c02304008-15 06 Jun 2022

Page 63 of 241

Trial Protocol Version 12 Proprietary confidential information. © 2022 Boehringer Ingelheim International GmbH or one or more of its affiliated companies. All rights reserved.

In phase Ib and phase II of the study at least 10 mL blood will be taken from a forearm vein at those time points specified in the Flow Chart and immediately shipped to a CRO with given authorization by BI.

Measurements and analysis will be made to determine the maximum decline in CTC counts compared to baseline that occurs at any point after treatment start. CTC response will be measured by a CTC reduction compared to baseline: CTC decline from ≥5 to <5 cells per 7.5 ml blood (R14-0865) for at least one time point after treatment start will be reported, as will all declines in CTC counts of 30% or more.

5.1.3 **Central Imaging**

Until the primary analysis, image data collection in phase II will be sent to a central imaging unit to obtain an independent blinded confirmation of tumour response assessment based on a uniform interpretation of radiographic image for all patients entered on to the trial. Upon receipt of image data, the central imaging unit will log all data onto a tracking system and perform quality control of digitised radiographic images.

An independent review of radiographic images including: (i) sequential lesion selection and measurement, (ii) incremental radiological response assessment followed by, (iii) global review of tumour response or progression, will be performed by blinded (with regard to patient, treatment, and visit) radiologist.

The review of the image data will be performed by independent radiologists, who are not affiliated with the study. All procedures will be done according to the specifications provided in the investigator site file. The purpose of the blinded reading is to independently assess patient response to therapy and disease progression (for details, please refer to the ISF).

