In case there is no value within this timeframe (day 84 to 92), but the patient discontinued all treatments earlier than day 84, then the End of Treatment (EOT) value should be used. A PSA value will be taken as EOT value if the assessment was performed between the date of discontinuation of the last study medication until 7 days (included) after this date (according to the protocol schedule for the EOT visit (EOTV)).

In case there is no value within this timeframe (day 84 to 92), and the patient did not discontinue all treatments earlier than day 84, no earlier value will be taken as replacement, the assessment will be missing.

PSA response

PSA response is defined as a decline in PSA value >50% (with confirmation at least 3 weeks later) (R13-1642). See Section 5.1.2. for more details.

Changes in CTC response

Changes in CTCs will be evaluated using the following criteria:

- CTC reduction is defined as a decline in CTC value from ≥5 to <5 cells per 7.5mL blood (called "specimen volume" within this section and Section 7.5.2.3) (R14-0865), for at least one post-baseline time-point. Patients with a CTC value <5 cells per 7.5 mL blood at baseline, or with missing baseline value, are not taken into consideration for this endpoint.
- Maximum decline in CTC counts (in number of cells) compared to baseline that occurs at any point after treatment start, defined as the difference (absolute and percentage) between the minimum post-baseline CTC value and the baseline CTC value. Patients with missing baseline value are considered missing for this criterion.
- CTC status at week 12 (≥5 or <5 cells per 7.5mL blood)

Baseline value is the value collected before a patient starts treatment with trial medication. Patients with no post-baseline value are considered as missing for the three criteria.

For the criterion "CTC status at week 12", the nearest assessment to C4V1 (day 85) will be used, with following window:

- A later value, until one week after (day 92), can be used
- An earlier value, after four weeks in trial (day 29), can be used.

In case the patient discontinued the trial before the planned assessment, the EOT assessment will be used for this criterion in case it is the nearest to the target day.

In case it is needed for descriptive tables, multiple entries for one single time point in a patient will be assessed as follows:

- If only one valid value (with acceptable specimen volume or imputable value) is available, this one will be used

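### SAP 5.2.2.2 defines expansion-cohort CTC response with ≤5 cells where the protocol and SAP 5.2.2.3 use <5; the rules differ only when the lowest count is exactly 5 from a baseline of 6 or more

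*SAP*

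**What the plan says.** The two documents state the CTC threshold in several places.

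- SAP 5.2.2.2, expansion cohort: "This is defined as a decline in CTC value from ≥ 5 to ≤ 5 cells per 7.5mL blood", for at least one time point after baseline. On eligibility for the endpoint it adds: "Patients with a CTC value <5 cells per 7.5 ml blood at baseline, or with missing baseline value, are not taken into consideration for this".
- Protocol 5.1.1.1, same endpoint and cohort: "CTC decline from ≥5 to <5 cells per 7.5ml blood".
- Protocol 5.1.1.2, phase II: the same ≥5 to <5 cut.
- Protocol 5.1.2.3, written for phase Ib and phase II together: "CTC decline from ≥5 to <5 cells per 7.5 ml blood (R14-0865) for at least one time point after treatment start will be reported".
- SAP 5.2.2.3, phase II: "CTC reduction is defined as a decline in CTC value from ≥5 to <5 cells per 7.5mL blood". The week 12 status there is also split into ≥5 and <5.

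All these statements of the decline criterion cite the same source, R14-0865. SAP 4.2, which lists departures from the protocol, names one for CTC: the added week 12 status. SAP 7.5.2.2, the analysis section for this cohort, says that frequencies of CTC reduction will be shown but does not restate the cut-off.

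**The concern.** Under SAP 5.2.2.2 as it reads, the value 5 sits on both sides of the cut. At baseline it keeps a patient in the ≥5 group, because only counts below 5 are set aside. After baseline it can count as a response. A patient who falls from 6 to 5 has not left the ≥5 category, yet the SAP scores him as a responder. The protocol scores the same patient as a non-responder.

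SAP 5.2.2.2 is the operative definition for this cohort, so someone deriving the endpoint from it could program a rule that differs from the protocol. Any error would run in one direction, towards more responders on a named secondary endpoint.

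**Working it through.** The plan gives no figure for this point, so there is nothing to reproduce. The check compares the two rules and then finds the patients on whom they disagree.

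**Inputs.** Let b be the baseline count, with b ≥ 5 required by SAP 5.2.2.2. Let p be the lowest post-baseline count. One qualifying time point is enough, so the lowest count decides the outcome.

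**Rules.**
- Rule A (protocol 5.1.1.1 and SAP 5.2.2.3): response if p < 5 and p < b.
- Rule B (SAP 5.2.2.2 as it reads): response if p ≤ 5 and p < b.

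Both rules require a decline, hence p < b.

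**Where they differ.** If p ≤ 4, both give a response. If p ≥ 6, neither does. If p = 5, rule A gives no response, and rule B gives one only if b > 5.

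| Baseline b | Lowest count p | Rule A | Rule B |
|---|---|---|---|
| 5 | 5 | no | no (no decline) |
| 6 | 5 | no | **yes** |
| 10 | 5 | no | **yes** |
| 10 | 4 | yes | yes |
| 10 | 6 | no | no |

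Enumerating every whole-number pair with b from 5 to 40 and p from 0 to 40 gives 36 × 41 = 1,476 pairs. The rules disagree on 35 of them. All 35 have p = 5, with b running from 6 to 40.

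**Can volume scaling create a 5?** SAP 7.5.2.2 scales a count only when the specimen is at least 5 mL and below 7.5 mL and at least 10 cells were counted:

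scaled count = 7.5 / volume × measured count

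With volume below 7.5 and a count of at least 10, the result is always above 10. For example, 10 cells in 7.4 mL give 7.5 / 7.4 × 10 = 10.14. Scaling therefore never produces a 5, and the disagreement arises from a measured 5 in a full specimen.

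**Effect on the reported proportion.** Each patient on whom the rules disagree adds one responder under rule B, which is a shift of 1/n. Here n is the number of patients in the denominator, that is, those with baseline ≥5. The documents plan about 25 patients but do not say how many will have baseline ≥5, so n is assumed:

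| Assumed n | Shift per patient |
|---|---|
| 25 | 1/25 = 4.0 points |
| 21 | 1/21 = 4.8 points |
| 15 | 1/15 = 6.7 points |
| 10 | 1/10 = 10.0 points |

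The documents give no distribution of CTC counts, so the expected number of such patients cannot be derived from them.

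**The case against.** The strongest reply is that no different rule was meant.

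- **It may not be on the page.** The text available was extracted from PDF, and a < may have been read as ≤. The spacing of this line differs from that of the parallel definitions. The protocol's lymph-node rule in 5.1.2.1 shows a similar pattern, with 20 mm on both sides of the cut. This makes a reading error plausible but does not establish it.
- **If it is on the page, it is most likely a typing slip.** The eligibility sentence uses <5, the cited source is the same, SAP section 3 says that the plan follows the protocol, and no change is declared. SAP 7.5.2.2 also speaks of CTC reduction, the term that SAP 5.2.2.3 defines with <5.
- **Little depends on it.** The endpoint is tabulated as frequencies in a single-arm cohort, without a test. Protocol 3.2 says that the cohort's results do not affect whether phase II continues.

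Most of this stands. It explains how the line probably arose and why the consequence is small. It does not remove the conflict in the text: nothing in the analysis section repeats the cut-off, so the definition section still needs to be right.

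**Conclusion.** As supplied, SAP 5.2.2.2 conflicts with protocol 5.1.1.1 and 5.1.2.3 and with SAP 5.2.2.3, and the conflict is undeclared. It affects only patients with baseline 6 or more whose lowest later count is exactly 5. It can only add responders, at 1/n each. The primary endpoint, the sample size and the error rates do not depend on it.

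Three stronger readings are tempting, and the documents support none of them.

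- **That every post-baseline count of 5 becomes a response.** A decline is required, so 5 to 5 is a non-response under both rules. Anyone who reaches 4 or fewer at any draw is a responder under both.
- **That the response rate is inflated by a known, sizeable amount.** Any such figure needs an assumed count distribution and an assumed number of eligible patients, and neither is given. A Poisson model would be a doubtful choice, since SAP 7.9.3 describes CTC counts as overdispersed.
- **That a planned comparison with phase II is spoiled.** None is planned. Protocol 7.3.4 has the expansion cohort and phase II analysed separately, and their populations differ by prior treatment.

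The conclusion assumes that the line reads ≤ in the SAP itself. If it reads < there, no discrepancy remains.

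**What to change.** 1. Check SAP 5.2.2.2 on the source page.
2. If it reads ≤, change the criterion to: from ≥5 to <5 cells per 7.5 mL blood. This matches protocol 5.1.1.1 and SAP 5.2.2.3.
3. Confirm that the programmed derivation for the expansion cohort uses <5.
4. If ≤5 was in fact intended, declare and justify it in SAP 4.2 as a departure from the protocol.

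The cost is one character in the SAP and a brief check of the derivation code. No data collection or other analysis changes.
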